### 9.3.2. Laboratory Value Summaries

Clinical laboratory tests, including hematology, serum, and chemistry, will be performed for each participant per the schedule of assessments. If specific safety issues arise, additional unscheduled laboratory tests/analyses will be performed at the discretion of the investigator.

All test results and associated normal ranges from central laboratories will be reported in SI units. All tests with numeric values will have a unique unit per test.

For test results that will be summarized with available normal ranges, the number and percentage of participants with the laboratory values being low, normal, high, and missing will be tabulated for each test and each visit.

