5.1. Inclusion Criteria

Participants are eligible to be included in the study only if all of the following criteria apply:

- 1. Ability to comprehend and willingness to sign a written ICF for the study.
- 2. Men or women, age \geq 18 years at the time of signing the ICF.
- 3. Diagnosis of primary wAIHA based on the presence of hemolytic anemia and serological evidence of anti-erythrocyte antibodies, detectable by a DAT positive for IgG only or IgG plus C3d.
 - *Note:* A DAT performed at screening is preferred; however, prior documentation of DAT results within 3 months of randomization is permitted.
- 4. Participants who were inadequately controlled with, were intolerant to, or have a contraindication to other therapies. There is no limit to the number of prior treatment regimens.
- 5. Hemoglobin \geq 6.5 to < 10 g/dL with symptoms of anemia as assessed by the investigator at screening (hemoglobin as determined by local laboratory).
- 6. FACIT-F score \leq 43 at screening.
- 7. Willingness to avoid pregnancy or fathering children based on the criteria below.
 - a. Male participants with reproductive potential must agree to take appropriate precautions to avoid fathering children (with 99% certainty) from screening through 90 days after the last dose of study drug and must refrain from donating sperm during this period. Permitted methods in that are at least 99% effective preventing pregnancy (see Appendix A) should be communicated to the participants and their understanding confirmed.
 - b. Female participants who are WOCBP must have a negative serum pregnancy test at screening and a negative urine pregnancy test before randomization and must agree to take appropriate precautions to avoid pregnancy (with 99% certainty) from screening through 90 days after the last dose of study drug and must refrain from donating oocytes during this period. Permitted methods that are at least 99% effective preventing pregnancy (see Appendix A) should be communicated to the participants and their understanding confirmed.
 - c. A female participant not considered to be of childbearing potential as defined in Appendix A is eligible.
 - *Note:* This criterion does not apply to women of nonchildbearing potential (i.e., surgically sterile with a hysterectomy and/or bilateral oophorectomy OR

- postmenopausal, defined as amenorrhea at least 12 months before screening, confirmed by FSH levels at screening).

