- 15. Participants who, in the opinion of the investigator, are unable or unlikely to comply with the dose regimen and study evaluations.
- 16. Any condition that would, in the investigator's judgment, interfere with full participation in the study, including administration of study drug and attending required study visits; pose a significant risk to the participant; or interfere with interpretation of study data.

- 17. Prior treatment with parsaclisib or another PI3Kδ, or a pan-PI3K inhibitor for any indication.
- 18. Participants with laboratory values at screening defined in Table 7.

Table 7: Exclusionary Laboratory Values

Lal	boratory Parameter ^a	Exclusion Criterion	
He	matology		
a	Platelets	$\leq 100 \times 10^9 / L$	
b	ANC	$\leq 1.5 \times 10^9/L$	
с	WBCs	$\leq 1.5 \times 10^9/L$	
He	patic		
d	ALT	≥ 2 × ULN	
e	AST	≥ 2 × ULN unless clearly related to active hemolysis	
Rei	Renal		
f	eGFR using 2021 CKD-EPI (Inker et al 2021)	≤ 45 mL/minute/1.73m ²	

^a If the central laboratory is unable to perform the test due to hemolysis related to wAIHA or the analytical method, then local laboratory test results may be used to determine participant eligibility.

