10.3.3. Safety Analyses

Safety analyses will be conducted for the safety population. Adverse events will be coded by the MedDRA dictionary, and TEAE (ie, AEs reported for the first time or worsening of a pre-existing event after first dose of study drug) will be tabulated by preferred term and system organ class for all events, related events, and events of Grade 3 or higher. Quantitative safety variables and their changes from baseline (laboratory, vital signs, etc) will be summarized with descriptive statistics. Clinically notable abnormal values will be flagged and tabulated based on predefined criteria.

The clinical laboratory data will be analyzed using summary statistics; no formal treatment group comparisons are planned. In addition, distributions of key laboratory parameters may be plotted over time; these values will also be classified into CTCAE toxicity grades, and tabulated. Descriptive statistics and mean change from baseline will be determined for vital signs at each assessment time. Vital sign results will be reviewed for clinically notable abnormalities.

Descriptive statistics and mean change from baseline will be determined for each ECG parameter at each assessment time. Electrocardiogram results will be reviewed for clinically notable abnormalities according to predefined criteria (see Table 14). Participants exhibiting clinically notable ECG abnormalities will be listed.

Table 14: Criteria for Clinically Notable Electrocardiogram Abnormalities

Parameter	High Threshold Low Threshold	
QTcF	> 460 ms	< 295 ms
PR	> 220 ms < 75 ms	
QRS	> 120 ms	< 50 ms
QT	> 500 ms	< 300 ms
RR	> 1330 ms	< 600 ms

QTcF = Fridericia correction.

Measures of exposure of parsaclisib will be summarized by means of summary statistics.

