### 9.2. Adverse Events

#### 9.2.1. Adverse Event Definitions

A TEAE is any AE either reported for the first time or worsening of a pre-existing event after first dose of study drug and within 30 days of the last dose of study drug. Analysis of AEs (as discussed below) will be limited to TEAEs, but data listings will include all AEs regardless of their timing in relation to study drug dose administration.

Adverse events will be tabulated by MedDRA PT and SOC. Severity of AEs will be graded using the National Cancer Institute CTCAE v5. The CTCAE reporting guidelines and grading details are available on the Cancer Therapy Evaluation Program website.

The subset of AEs considered by the investigator to be related to study drug will be considered treatment-related AEs. If the investigator does not specify the relationship of the AE to study drug, the AE will be considered to be treatment-related. The incidence of AEs and treatment-related AEs will be tabulated. Serious AEs will also be tabulated.

Any missing onset date, causality, or severity must be queried for resolution. Unresolved missing causality and severity will be handled according to the following rules:

- An unresolved missing causality will be considered treatment-related.
- An unresolved missing severity will be identified as an unknown severity.

For purposes of analysis, all AEs will be considered TEAEs unless the AE can unequivocally be defined as not treatment-emergent.

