## 9.3. Clinical Laboratory Tests

### 9.3.1. Laboratory Value Definitions

Laboratory values and change from baseline will be summarized descriptively by central laboratory. Baseline will be determined according to Section 4.1.3, with exceptions listed below, in which case the investigative site laboratory or an accredited local laboratory may be used:

- Hematology panels (ie, complete blood count and differential count), will be sent to a local laboratory for analysis.
- Participant management, which includes dose modification, serious adverse event, or COVID-19 restrictions (eg, travel), for local laboratory assessments deemed necessary by the investigator for participant management. Note: Such assessment data and reference ranges must be recorded in the participant's eCRF.

In the event both local and central laboratory assessments are available, local laboratory assessment will be used for analysis. Laboratory values, change from baseline values, and percent change from baseline values will be summarized descriptively by visit. Baseline values will be determined using the nonmissing values collected before the first administration, prioritizing scheduled assessments over unscheduled visits. For baseline laboratory values with the same date and time in the same priority category, additional rules may be provided following consultation with the medical monitor to delineate the value that will be defined as baseline.

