### 11.1. Changes to Protocol-Defined Analyses

On 17 APR 2023, Incyte decided to terminate this Phase 3 study. The decision was based on change in the regulatory landscape for Pi3k-delta inhibitors combined with enrollment challenges.

With limited enrollment in each treatment group, as well as participant option for early crossover (to parsaclisib), most of the Protocol-defined statistical analyses on efficacy endpoints will not be applicable; therefore, summary statistics will only be provided for hemoglobin response and FACIT-F scores and listings will only be provided for all other efficacy endpoints. Additionally, no p-values will be provided and no statistical comparisons will be made.

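### The SAP text and planned table titles omit the CTCAE grading of key laboratory values that Protocol 10.3.3 promises; the low/normal/high display in SAP 9.3.2 cannot show severity, and SAP 11.1 does not record the change

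*SAP*

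**What the plan says.** Protocol 10.3.3 (Safety Analyses) makes plots of key laboratory parameters optional, but uses firm wording for grading: "these values will also be classified into CTCAE toxicity grades, and tabulated". It does not define which parameters are key.

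SAP 9.3.2 (Laboratory Value Summaries) gives one categorical summary. Where a normal range exists for a test, the plan is that "the number and percentage of participants with the laboratory values being low, normal, high, and missing will be tabulated", separately by test and by visit. SAP 9.3.1 adds a continuous summary: "Laboratory values, change from baseline values, and percent change from baseline values will be summarized descriptively by visit". In the SAP, CTCAE is applied to adverse events: "Severity of AEs will be graded using the National Cancer Institute CTCAE v5" (SAP 9.2.1). Appendix A plans two laboratory tables, 3.3.1 (hematology) and 3.3.2 (chemistry). Neither title names a grade or a shift from baseline.

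SAP 11.1 (Changes to Protocol-Defined Analyses) is confined to efficacy: "most of the Protocol-defined statistical analyses on efficacy endpoints will not be applicable". It says nothing about laboratory grading.

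**The concern.** SAP Section 7 drops all p-values, so the descriptive safety summary carries much of the report. A protocol commitment on safety is missing from the SAP text, and the section meant to record such changes does not mention it.

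The remaining display suits this population poorly. Participants enter anemic. AST is exclusionary at "≥ 2 × ULN unless clearly related to active hemolysis" (Protocol Table 7), so a high AST can be a baseline state. SAP 9.3.1 sends hematology to local laboratories and prefers local over central values, so low and high depend on site ranges, whereas the ANC and platelet cut-offs in Protocol Table 9 are absolute. A reader who wants to know how many participants reached a given severity of neutropenia, thrombocytopenia or transaminase rise could not learn it from the categories in SAP 9.3.2.

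**Working it through.** The plan states no figure on this point, so there is none to reproduce. The check sorts example values twice: by the SAP categories and by the severity levels printed in Protocol Table 9. The documents give no normal limits, so those below are assumptions.

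**Inputs from Protocol Table 9 and Sections 5.1 and 9.6**
- ANC: Grade 3 at ≤ 1.0, Grade 4 at < 0.5 (× 10⁹/L).
- Platelets: Grade 2 at 50 to < 75, Grade 3 or higher at < 50 (× 10⁹/L).
- ALT and AST: Grade 2 at > 3 to 5 × ULN, Grade 3 or higher at > 5 × ULN. A value ≥ 5 × ULN is also an event of clinical interest.
- Hemoglobin at screening: 6.5 to < 10 g/dL.

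**Assumed lower normal limits:** ANC 1.5 to 2.0 × 10⁹/L; platelets 150 × 10⁹/L; hemoglobin 11.5 to 13.5 g/dL.

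| Test | Example values | SAP 9.3.2 category | Table 9 level |
|---|---|---|---|
| ANC (× 10⁹/L) | 1.4 / 0.8 / 0.4 | low / low / low | above the Grade 3 cut-off / Grade 3 / Grade 4 |
| Platelets (× 10⁹/L) | 101 / 74 / 49 | low / low / low | below Grade 2 / Grade 2 / Grade 3 or higher |
| ALT or AST (× ULN) | 1.1 / 3.5 / 5.1 | high / high / high | below Grade 2 / Grade 2 / Grade 3 or higher |

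The ANC result is the same at assumed limits of 1.5, 1.8 and 2.0. The ALT/AST result needs no assumption, because the values are multiples of the ULN.

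**Cut-offs readable from the categories.** Table 9 gives 2 for ANC + 2 for platelets + 2 for ALT + 2 for AST = 8. None coincides with a normal-range limit, so 0 of 8 can be read from the low/normal/high display. This count concerns that display only.

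**Hemoglobin.** With any lower limit from 11.5 to 13.5, every value in the entry range is low. A fall from 9.9 to 6.5 (9.9 − 6.5 = 3.4 g/dL) does not change category. A value of 10.0 to 11.4, which meets the 10 g/dL part of the response definition, is also still low. Recovery into the normal range does show.

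**Timing.** The SAP 9.3.2 table is by visit. Table 9 asks for weekly repeat ALT/AST and at least weekly ANC monitoring after an event, which falls largely between scheduled visits. The SAP gives no worst-value rule and does not say how unscheduled post-baseline laboratory values are handled.

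**The case against.** The case for leaving the plan alone has five parts.

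1. **Severity is visible elsewhere in the laboratory summary.** SAP 5.1 includes minimum, maximum and quartiles, and SAP 9.3.1 adds change from baseline. A reader might infer that a profound neutropenia and a trivial low value would be indistinguishable in the report. The documents do not support that: at a scheduled visit an extreme ANC would appear as the minimum. What stands is that these statistics do not count participants by grade.

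2. **The AE route.** Each of the eight Table 9 levels leads to an interruption of study drug, and Protocol 9.1 makes a laboratory result an AE if it requires a change in study drug. Such AEs are CTCAE-graded and feed Tables 3.2.5 and 3.2.8, whether or not the value came from a scheduled visit. This is a real mitigation, but incomplete. Table 9 is a guideline, its Grade 3 ANC row excepts underlying disease, and reporting depends on the investigator. Protocol 9.1 does not count disease worsening as an AE, so hemoglobin falls from hemolysis are not systematically captured. Table 3.2.5 also pools Grade 3 and above.

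3. **Absence is not proven.** The supplied listings stop at 2.2, before any safety listing. Tables 3.3.1 and 3.3.2 are marked as standard, and the standard shells are not in the documents. Grading could exist there. The point is therefore limited to SAP text and table titles, and it is an omission, not a stated decision to drop grading.

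4. **Delegation.** Protocol Section 10 leaves the final analyses to the SAP, and SAP 5.3 repeats in general terms that the protocol-defined analyses do not apply. The stated reasons are small numbers and early crossover. Neither prevents descriptive grading of values already collected.

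5. **Hemoglobin.** The entry limit applies at screening, while baseline is the last value before first dose. Improvement remains visible, and Table 2.1.1 covers hemoglobin response. The argument is therefore one-sided (worsening only) and rests on an assumed normal limit.

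A reader might also turn one severe value into a per-arm toxicity rate. The documents do not give the arm sizes. SAP Section 1 reports 13 dosed, and the ratio moved from 1:1 to 2:1 at Amendment 1, so the parsaclisib arm could be anywhere from about 13 × 1/2 = 6.5 to 13 × 2/3 = 8.7. Given the first two parts, such a value need not be hidden either. No rate should be quoted.

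**Conclusion.** The point holds in limited form. The SAP text and planned table titles omit a grading and tabulation that Protocol 10.3.3 promises, and SAP 11.1 does not record it. The display that SAP 9.3.2 does describe resolves 0 of the 8 Table 9 severity cut-offs for ANC, platelets, ALT and AST. If the lower normal limit for hemoglobin is above 10 g/dL, it cannot show worsening from the entry range. The by-visit statistics and graded AE tables recover part of this. What is missing is a systematic count of participants by worst laboratory grade.

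The ANC and platelet parts rest on assumed lower normal limits. The whole point is conditional on the unseen shells and listings not already supplying grades. It deserves correction because safety is most of what this terminated trial can report and the correction is small, not because a severe toxicity would necessarily go unseen.

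**What to change.** In SAP 9.3.2 and Appendix A, for hemoglobin, ANC, platelets, ALT and AST:

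- Add a table of baseline against worst on-treatment CTCAE v5.0 grade, with unscheduled values included.
- Add a listing of all Grade 3-4 laboratory values. With about 13 participants this listing alone may be enough; SAP 9.1 already allows listings in place of tables.
- State in SAP 9.3.2 which parameters are key, since Protocol 10.3.3 does not. The five above are a proposal. The baseline cross-classification and the unscheduled values go beyond the protocol's wording, but make the grades interpretable in participants who enter with abnormal values.
- Record any remaining departure from Protocol 10.3.3 in SAP 11.1, with the reason. If the standard shells or the safety listings already give grades, a cross-reference in SAP 9.3.2 would settle that part.

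The cost is one extra table and one listing. No new data are needed, and CTCAE v5.0 is already the trial's grading system for AEs.

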## 9.4. Vital Signs

Descriptive statistics and mean change from baseline will be determined for vital signs (blood pressure, pulse, respiratory rate, and body temperature) at each assessment time.

Criteria for clinically notable vital sign abnormalities are defined in [Table 2](#). The abnormal values for participants exhibiting clinically notable vital sign abnormalities will be listed along with their assigned treatment group. Alert vital signs are defined as an absolute value outside the defined range and percentage change > 25%. The abnormal values for participants exhibiting alert vital sign abnormalities will be listed.

**Table 2: Criteria for Clinically Notable Vital Sign Abnormalities for  $\geq 18$  Years Old**

Parameter	High Threshold	Low Threshold
Systolic blood pressure	$> 155$ mmHg	$< 85$ mmHg
Diastolic blood pressure	$> 100$ mmHg	$< 40$ mmHg
Pulse	$> 100$ bpm	$< 45$ bpm
Temperature	$> 38^{\circ}\text{C}$	$< 35.5^{\circ}\text{C}$
Respiratory rate	$> 20$ breaths/min	$< 8$ breaths/min

## 9.5. Electrocardiograms

Descriptive statistics and mean change from baseline will be summarized for each ECG parameter at each assessment time. Electrocardiogram results will be reviewed for clinically notable abnormalities according to predefined criteria (see [Table 3](#)). Participants exhibiting clinically notable ECG abnormalities will be listed.

**Table 3: Criteria for Clinically Notable Electrocardiogram Abnormalities**

Parameter	High Threshold	Low Threshold
QTcF	$> 460$ ms	$< 295$ ms
PR	$> 220$ ms	$< 75$ ms
QRS	$> 120$ ms	$< 50$ ms
QT	$> 500$ ms	$< 300$ ms
RR	$> 1330$ ms	$< 600$ ms

## 10. INTERIM ANALYSES

No formal interim analysis is planned in this study.

## 11. CHANGES AND MODIFICATIONS TO THE ANALYSIS PLAN

All versions of the SAP are listed in [Table 4](#).

**Table 4: Statistical Analysis Plan Versions**

SAP Version	Date
Original	17 JAN 2024

### 11.1. Changes to Protocol-Defined Analyses

On 17 APR 2023, Incyte decided to terminate this Phase 3 study. The decision was based on change in the regulatory landscape for Pi3k-delta inhibitors combined with enrollment challenges.

With limited enrollment in each treatment group, as well as participant option for early crossover (to parsaclisib), most of the Protocol-defined statistical analyses on efficacy endpoints will not be applicable; therefore, summary statistics will only be provided for hemoglobin response and FACIT-F scores and listings will only be provided for all other efficacy endpoints. Additionally, no p-values will be provided and no statistical comparisons will be made.

### 11.2. Changes to the Statistical Analysis Plan

Not applicable.

## APPENDIX A. PLANNED TABLES AND LISTINGS

This appendix provides a list of the planned tables and listings for the Clinical Study Report. Shells are provided in a separate document for tables that are not in the most current Standard Safety Tables v1.13.

The list of tables and listings are to be used as guidelines. Modifications of the lists that do not otherwise affect the nature of the analysis will not warrant an amendment to the SAP.

### Tables

Table No.	Title	Population	Standard
Baseline and Demographic Characteristics			
1.1 Disposition			
1.1.1	Analysis Populations	Safety	X
1.1.2	Summary of Participant Disposition	Safety	X
1.2 Demography			
1.2.1	Summary of Demographics	Safety	X
1.3 Baseline Characteristics			
1.3.1	Summary of Baseline Disease Characteristics	Safety	X
1.4 Prior Medication and Concomitant Medication			
1.4.1	Summary of Prior Medications	Safety	X
1.4.2	Summary of Prior Medications for wAIHA	Safety	X
1.4.3	Summary of Concomitant Medications	Safety	X
1.5 Others			
1.5.1	Summary of General Medical History	Safety	X
1.5.2	Summary of wAIHA History	Safety	X
1.5.3	Summary of Protocol Deviations by Category	Safety	X
Efficacy			
2.1 Primary and Key Secondary Efficacy			
2.1.1	Summary of Participants With Hemoglobin $\geq 10$ g/dL With an Increase From Baseline of $\geq 2$ g/dL	Safety	
2.1.2	Summary of Participants With a $\geq 3$ -Point Increase From Baseline in FACIT-F Score at Week 24	Safety	
Safety			
3.1 Study Drug Exposure			
3.1.1	Summary of Drug Compliance	Safety	X
3.1.2	Summary of Study Drug Exposure	Safety	X
3.1.3	Summary of Daily Usage of Prednisone	Safety	X
3.2 Adverse Events			
3.2.1	Overall Summary of Treatment-Emergent Adverse Events	Safety	X
3.2.2	Summary of Treatment-Emergent Adverse Events by MedDRA System Organ Class and Preferred Term	Safety	X
3.2.3	Summary of Treatment-Emergent Adverse Events by MedDRA Preferred Term in Decreasing Order of Frequency	Safety	X
3.2.4	Summary of Treatment-Related Treatment-Emergent Adverse Events by MedDRA System Organ Class and Preferred Term	Safety	X

Table No.	Title	Population	Standard
3.2.5	Summary of Grade 3 or Higher Treatment-Emergent Adverse Events by MedDRA System Organ Class and Preferred Term	Safety	X
3.2.6	Summary of Treatment-Emergent Adverse Events With a Fatal Outcome by MedDRA System Organ Class and Preferred Term	Safety	X
3.2.7	Summary of Serious Treatment-Emergent Adverse Events by MedDRA System Organ Class and Preferred Term	Safety	X
3.2.8	Summary of Treatment-Emergent Adverse Events Leading to Dose Interruption by MedDRA System Organ Class and Preferred Term	Safety	X
3.2.9	Summary of Treatment-Emergent Adverse Events Leading to Discontinuation of Study Drug by MedDRA System Organ Class and Preferred Term	Safety	X
3.3 Laboratory			
3.3.1	Summary of Laboratory Values - Hematology	Safety	X
3.3.2	Summary of Laboratory Values - Chemistry	Safety	X
3.4 Vital Signs			
3.4.1	Summary of Systolic Blood Pressure	Safety	X
3.4.2	Summary of Diastolic Blood Pressure	Safety	X
3.4.3	Summary of Pulse	Safety	X
3.4.4	Summary of Respiratory Rate	Safety	X
3.4.5	Summary of Body Temperature	Safety	X
3.5 ECG			
3.5.1	Summary of PR Interval (ms) From 12-Lead ECG	Safety	X
3.5.2	Summary of QRS Interval (ms) From 12-Lead ECG	Safety	X
3.5.3	Summary of QT Interval (ms) From 12-Lead ECG	Safety	X
3.5.4	Summary of QTcF Interval (ms) From 12-Lead ECG	Safety	X
3.5.5	Summary of RR Interval (ms) From 12-Lead ECG	Safety	X
3.5.6	Summary of Clinically Significant ECG Abnormality	Safety	X

